6.4.9 Resource use measures & the EQ-5D-5L

Resource use (e.g. procedure costs, length of stay, readmission etc) QALYs (derived from EQ-5D-5L and mortality data) and cost-effectiveness analyses will be detailed in a separate health economics plan.

6.5 Subgroup analysis

Sub-group analyses will investigate whether the relative effects of OO and LAO differ according to:

- Whether a patient underwent neoadjuvant chemotherapy/chemoradiotherapy versus no neoadjuvant treatment prior to surgery.
- POSSUM physiological score assessed at recruitment.
- BMI assessed at recruitment.

Separate treatment effect estimates and 95% confidence intervals will be presented for those undergoing neoadjuvant treatment and those who do not, and for those above or at the median and those below the median POSSUM score and BMI. The evidence for a modification of the true treatment by each of the above three measures in turn will be quantified by adding an interaction term to the above primary analysis model. For neoadjuvant treatment the interaction term will be a binary covariate distinguishing those

participants who underwent any neoadjuvant treatment and were allocated to the LAO group. For POSSUM score and BMI, the interaction term will be equal to the POSSUM score or BMI if the participant is in the LAO group, zero otherwise.

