6.3 Primary analysis

The null hypothesis being addressed by the primary analysis is that, in truth, physical functioning in the three months following randomisation, measured with the physical function scale of the QLQ-C30, is identical whether access for a patient’s oesophagectomy was achieved with LAO or OO.

Using the full analysis set, the following analysis will be conducted separately for feasibility and full trial patients:

The relative effectiveness of the two approaches will be quantified as a difference in mean response on the physical function scale of the QLQ-C30 (LAO mean – OO mean), amongst patients in the full analysis set, using patients’ available measures from the three-week and six-week post-surgery, and the three-month post-randomisation assessments. The difference in mean response will be presented with its 95% confidence interval, and p-value.

The difference in means will be estimated in a mixed effects linear regression model with patient response at three-week (y_{i1}) and six-week (y_{i2}) post-surgery, and three-month (y_{i3}) post-randomisation as the outcome variables (i.e. between one and three outcome measurements per patient), and covariates: treatment allocation ($x_{1i}=1$: LAO; $x_{1i}=0$: OO), baseline physical function (x_{2i}), dummy variables distinguishing centres ($x_{3ki}=0,1$; $k=1,\dots,K$ indexing the centres), two dummy variables distinguishing assessment points ($x_{4ti}=0,1$; $t=1,2,3$), and a dummy variable distinguishing patients who underwent neoadjuvant treatment or not ($x_{5i}=1$: underwent neoadjuvant treatment; $x_{5i}=0$: no neoadjuvant treatment). Finally a dummy variable distinguishing those participant without a baseline assessment of outcome ($x_{6i}=1$: no baseline assessment; $x_{6i}=0$: baseline assessment available). A normally distributed random effect will accommodate the correlation between each patient’s responses: $z_i \sim N(0, \sigma_z)$. A normal distribution is assumed for the residual errors: $e_i \sim N(0, \sigma_e)$. The coefficient for the treatment allocation covariate (β_1) is the intention to treat estimate of treatment effectiveness, comparing LAO to OO. In statistical notation:

$$y_{it} = \beta_0 + \beta_1 x_{1i} + \beta_2 x_{2i} + \sum_{k=1}^K \beta_{3k} x_{3ki} + \sum_{t=1}^3 \beta_{4t} x_{4ti} + \beta_5 x_{5i} + \beta_6 x_{6i} + z_i + e_i$$

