9.2 POSSUM Physiological Score

The POSSUM Physiological score(11) is derived from the following physiological measures pre-surgery, with higher scores indicating poorer health:

- Age in years
- Cardiac signs
- Respiratory history
- Chest radiograph
- Systolic blood pressure
- Pulse
- Glasgow coma score
- Haemoglobin
- White cell count
- Urea
- Sodium
- Potassium
- Electrocardiogram

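### The POSSUM and BMI interaction tests omit the score's main effect, so residual prognostic effect can be reported as treatment-effect modification

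*SAP*

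**What the plan says.** SAP Section 6.5 names three potential effect modifiers: neoadjuvant treatment, POSSUM physiological score and BMI. Evidence for modification by each is to be obtained by "adding an interaction term to the above primary analysis model". For the two continuous scores the term is defined exactly: "the interaction term will be equal to the POSSUM score or BMI if the participant is in the LAO group, zero otherwise". Supplementary Table 2 has a line for each interaction p-value.

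Section 6.3 sets out the primary model in words and as an equation. Its covariates are treatment allocation, then "baseline physical function (x_{2i}), dummy variables distinguishing centres", assessment-point dummies, "a dummy variable distinguishing patients who underwent neoadjuvant treatment or not", and a missing-baseline indicator, which closes the list: "Finally a dummy variable distinguishing those participant without a baseline assessment of outcome". POSSUM and BMI are not in it, and no other section adds them.

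Section 9.2 describes the POSSUM score as derived from pre-surgery measures, "with higher scores indicating poorer health".

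**The concern.** An interaction test asks whether the slope of outcome on the score differs between arms, so both slopes must be free to vary. The model as specified estimates the slope in LAO only and sets the slope in OO to zero. If the score predicts recovery equally in both arms, with the same treatment benefit for everyone, the coefficient is still non-zero and is labelled an interaction.

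POSSUM summarises physiological health, so some association with post-operative physical function beyond the baseline score is plausible. The risk is a published statement that LAO suits, or fails, patients with poorer physiology or higher BMI when the data show only that such patients recover differently whichever access is used. The opposite error is also possible: a true interaction goes unseen if it happens to leave the LAO slope near zero.

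**Working it through.** **1. The algebra.** Let T = 1 for LAO and 0 for OO, and let P be the score. Suppose that, given the primary-model covariates, the mean outcome is a + b·T + d·P + t·T·P, where d is the residual prognostic slope and t the true interaction.

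| | slope in OO | slope in LAO | coefficient of T·P |
|---|---|---|---|
| Truth | d | d + t | t |
| Section 6.5 as written (no P) | fixed at 0 | g | g estimates d + t |
| With P added | d | d + t | t |

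The test as written therefore addresses d + t = 0, not t = 0. The neoadjuvant interaction does not share the fault, because its main effect (x5) is already in the Section 6.3 model.

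**2. The plan's own figures.** The SAP gives no figure for the interaction tests. Its sample size in Section 2.7 reproduces: 0.4 × 0.85 = 0.34, and 2 × (1.960 + 1.282)² / 0.34² = 181.8, hence 182 per group and 364 in total. Dividing 182 by 0.9 gives 202.2, hence 203 per group and 406 in total. Section 2.7 also expects 300 main-study and about 120 feasibility patients, or 420. With 10% missing, that leaves 270 + 108 = 378.

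**3. Closed-form size of the error when t = 0.** Let r be the assumed residual partial correlation of score with outcome and m the number of LAO patients. The test statistic centres near r × √m / √(1 − r²). The two-sided 5% test then rejects with probability Φ(centre − 1.96) + Φ(−centre − 1.96).

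| r (assumed) | centre, m = 210 | rejection | centre, m = 189 | rejection |
|---|---|---|---|---|
| 0 | 0 | 5% | 0 | 5% |
| 0.05 | 0.73 | 11% | 0.69 | 11% |
| 0.10 | 1.46 | 31% | 1.38 | 28% |
| 0.15 | 2.20 | 59% | 2.09 | 55% |
| 0.20 | 2.96 | 84% | 2.81 | 80% |
| 0.30 | 4.56 | 99.5% | 4.32 | 99% |

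**4. Simulation, no true interaction.** The pooled columns fit the two cohorts separately and combine them by inverse variance, as the SAP does for its primary estimate.

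| assumed residual slope or correlation | 270 + 108, pooled | 300 + 120, pooled | N = 364 | N = 406 |
|---|---|---|---|---|
| 0 | 5% | 5% | 5% | 5% |
| 0.05 | 11% | not run | 13% | 15% |
| 0.10 | 27% | 30% | 37% | 41% |
| 0.15 | 54% | 58% | 67% | 72% |
| 0.20 | 78% | 83% | 88% | 92% |
| 0.30 | 99% | 99% | 99.6% | 99.8% |

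With the main effect added, rejection is about 5% in every setting.

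The two right-hand columns are higher because there the slope is per single-visit residual SD while the analysis uses the mean of three visits. At the assumed intraclass correlation of 0.5, the residual SD of that mean is √(0.5 + 0.5/3) = 0.816. A slope of 0.20 then corresponds to a partial correlation of 0.20 / √(0.04 + 0.667) = 0.24. At slope 0.20 and N = 364, the rejection rate is 95% with intraclass correlation 0.3 and 82% with 0.7. The full random-intercept model (150 runs, slope 0.20) gave 87% without the main effect and 5% with it.

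**5. Missed interaction.** Take a slope of −0.2 in OO and 0 in LAO, so t = +0.2, with N = 364. The test as written has an average estimate of about zero and rejects in 5% of trials. With the main effect added, power is 63%.

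The prognostic slopes, the intraclass correlation, eight centres and 80% neoadjuvant treatment in the N = 364 and N = 406 runs are assumptions, not SAP figures.

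**The case against.** The strongest reply is that any trained analyst enters a covariate alongside its product with treatment, and that Section 6.5 defines only the coding of the product without forbidding the main effect. That may well happen. But the text says one term is added to a fully listed model, and Section 1 wants the plan to let someone else run the analysis. Section 5.6 promises to report departures only for the primary effectiveness analysis, so a silent repair here need not be declared.

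The second reply concerns reach, and it stands. Two interaction p-values in a supplementary table are affected, with no decision rule attached. A reader might infer that the trial's main conclusion is compromised. It is not: the primary pooled estimate, the sensitivity analyses and the neoadjuvant interaction do not use these terms.

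The third reply concerns certainty, and it also stands. A reader might infer that every prognostic effect of POSSUM or BMI will appear as effect modification. The documents do not support that. Only association left after baseline physical function, centre and neoadjuvant treatment enters the coefficient. If that is zero, the test keeps its 5% level. For BMI the SAP says nothing that implies a prognostic effect.

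A reader might also object that a p-value from the continuous score is printed beneath median-split estimates. Section 6.5 states this openly. Testing on the continuous scale and displaying by category is a common choice, not an error. Separate estimates fitted within each half carry the subgroup's main effect in their own intercepts and are sound.

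**Conclusion.** The point holds on the text. As specified, the POSSUM and BMI tests measure the score's slope in LAO rather than the difference in slopes between arms. This is a stated rule that gives the wrong test, not a missing detail. How often it misleads depends on a residual prognostic effect that the SAP does not give. Over the assumed range of 0 to 0.30, the false-positive rate of the nominal 5% test runs from 5% to about 99%. It is already 27-41% at 0.10. It should be corrected before analysis, but it is confined to two secondary p-values and does not threaten the primary result.

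**What to change.** In Section 6.5, state that each POSSUM or BMI interaction model adds to the Section 6.3 model both the score (centred) as a main effect and its product with allocation, and that the interaction p-value is taken from the product term. Centring does not change that p-value; it makes the treatment coefficient the effect at the average score. The neoadjuvant test and the median-split display need no change. The cost is one sentence in the SAP, an entry in its table of changes and one extra covariate in each of two models. No new data are needed.

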6.6 Sensitivity analysis

If, at one or more of the three time points contributing to the primary outcome, more than 20% of data is missing, the recorded reasons for missing data will be assessed, and data at the three time points imputed in accordance with those reasons. This imputed dataset will be the basis of a sensitivity analysis.

As participants whose surgery could not be completed are likely to be informed of this, the analysis of pain at six days post-surgery will be repeated using the per protocol set.

The primary outcome requires that the average time from randomisation to surgery is the same for the study groups being compared. We will conduct a sensitivity analysis, additionally adjusted for each patient's time from randomisation to surgery.

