2.7 Sample size and justification

The theoretical advantage of LAO compared to OO for patients is improved short-term recovery with the long-term survival benefit of surgery maintained. Consequently, the primary endpoint is the QLQ C30 Physical Function sub-scale measured at three and six-weeks post-surgery and three months post-randomisation.

For simplicity, and to indicate the minimum statistical power that will be achieved for the comparison of recovery, we consider just the six-week assessment of physical function. The planned analysis, based on the three-week, six-week, and three-month assessments of patient-reported physical function (primary outcome), and the baseline assessment as a covariate, is likely to have greater power than indicated here.

We are assuming that having adjusted analyses for centre, there will be no further need to accommodate clustering of outcomes by surgeon. In fact, as a team of surgeons is involved in each case (in decision-making, in-hospital care, and often in theatre), it would be difficult to do in practice.

A recent review of patient reported outcomes has indicated that the minimum clinically important difference on the QLQ-C30 Physical Function Scale is 0.4 standard deviations (1). Allowance for 5% of patients allocated to LAO undergoing OO, and 10% of patients in each group being found during surgery to have more extensive disease, can be achieved by reducing the effect size to be detected to 0.34 standard deviations. In this situation 182 patients in each group (364 patients in total) will allow a true treatment effect (LAO versus OO) of 0.4 standard deviations to be detected with 90% power at the 5% significance level, when up to 15% of patients are not able to follow their allocated procedure.

Further allowing for up to 10% missing outcome data, e.g. due to the patient being too sick, increases the target sample size to $364/0.9 = 406$ patients in total. Hence our sample size target for the definitive ROMIO trial is 203 patients allocated to LAO and 203 patients allocated to OO.

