3.3 Procedures for missing data

The primary effectiveness analysis will be based upon those randomised participants who provide at least one of the three post-treatment assessments of physical function contributing to the primary outcome.

The five QLQ-C30 items contributing to the physical function scale are as follows:

1. Do you have any trouble doing strenuous activities, like carrying a heavy shopping bag or a suitcase?
2. Do you have any trouble taking a long walk?
3. Do you have any trouble taking a short walk outside of the house?

4. Do you need to stay in bed or a chair during the day?
5. Do you need help with eating, dressing, washing yourself or using the toilet?

A patient will be considered to have completed the physical function scale and to have a score of zero (lowest level of physical functioning), if their reason for not having a physical function score is recorded as due to being in intensive care or having died prior to the questionnaire being due. This is a reasonable assumption about responses to the above five questions in those circumstances and is to prevent these values being implicitly imputed by the statistical model upon which the analysis is based. This approach will only be used for the physical function and role function scales, where the assumption of a zero value can be justified; the number of values imputed in this way will be reported by treatment group. The two items contributing to role function are:

6. Were you limited in doing either your work or other daily activities?
7. Were you limited in pursuing your hobbies or other leisure time activities?

Participants missing their baseline assessment of a patient reported outcome will be included in the analysis by (i) imputing the overall mean for the corresponding observed baseline measurements, (ii) including an indicator variable as a covariate with values 0 if the individual has provided a baseline measure, and value 1 if not. This approach has been shown to give unbiased estimates in a randomised trial, and to avoid the loss of power that a complete case analysis will cause(8).

When single items are missing from any of the patient reported outcomes, these will be addressed using the accepted guidelines where available.

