6.7 Exploratory/other analysis

For each scale from the patient reported outcomes, the mean response for LAO and OO groups at each assessment point up to 24 months will be presented graphically, with an indication of the number of patients in each group contributing to the estimates. Differences in quality of life are not expected to persist following the post-surgical recovery period. Any observed differences subsequent to three months post-randomisation will be noted in this exploratory analysis.

The Bang Blinding Index will be presented for both LAO and OO groups separately to assess the success of patient blinding to allocation in the first week post-surgery.

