8. FIGURES AND TABLES FOR JOURNAL PUBLICATION OF PRIMARY ANALYSIS

The following are the intended figures and tables for the main journal publications of the ROMIO results. Numbered tables and figures will be presented in the initial paper, those indexed by letters will appear in the subsequent paper.

Table 1. Baseline Characteristics by allocated surgery

	OO (n=)	LAO (n=)
Male; n (%)		
Mean age (SD), n		
Mean BMI (SD), n		
Mean POSSUM physiological score (SD), n		
WHO performance status score, n (%)		
0		
1		
2		
Tumour histologic findings; n (%)		
Adenocarcinoma		
Squamous cell carcinoma		
Adenosquamous		
Other		
Location of tumour in oesophagus; n (%)		
Upper third		
Middle third		
Lower third / Siewert I		
Junctional tumour, Siewert II		
Junctional tumour, Siewert III		
Clinical tumour classification; n (%)		
cT1		
cT2		
cT3		
cT4a		
Clinical node classification; n (%)		
cN0		
cN1		
cN2		
Neoadjuvant treatment; n (%)		
Chemotherapy		
Chemoradiotherapy		
None		

Table 2. Post-surgical recovery of physical function by allocated surgery (primary analysis)

	OO (n=)	LAO (n=)
PRIMARY ANALYSIS – pooled estimate		
Pre-randomisation mean (SD) n		
Three-week post-surgery mean (SD) n		
Six-week post-surgery mean (SD) n		
Three-month post-randomisation mean (SD) n		
Treatment effect (95% confidence interval) p-value		
SENSITIVITY ANALYSES		
Adjusted for time from randomization to surgery		
Treatment effect (95% confidence interval)		
Missing outcome data imputed		
Treatment effect (95% confidence interval)		

Table 3. Complications in those participants undergoing allocated surgery. Counts are of patients, who may have experienced more than one complication of a given type

	OO (n=)	LAO (n=)	p-value
Clavien-Dindo Classification of Complications, n (%)			
Normal recovery			
Grade I/II			
Grade IIIa / Grade IIIb			
Grade IVa / Grade IVb			
Grade V (death of patient)			
Key post-operative complications within 31 days of surgery, n (%)			
Oesophagoenteric leak from anastomosis, staple line, or localised conduit necrosis			
Conduit necrosis/failure			
Chyle leak			
Pneumonia / chest infection			
Delayed gastric emptying			
GI bleeding requiring intervention or transfusion			
Acute abdominal wall dehiscence/hernia			
Acute diaphragmatic hernia			
Key post-operative complications between 31 and 90 days of surgery, n (%)			
Oesophagoenteric leak from anastomosis, staple line, or localised conduit necrosis			
Conduit necrosis/failure			
Chyle leak			

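### The sensitivity analysis for missing primary-outcome data should not depend on a 20% trigger, and its imputation method should be stated

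*SAP*

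**What the plan says.** Section 6.6 contains the only planned check on missing primary-outcome data. It is conditional: "If, at one or more of the three time points contributing to the primary outcome, more than 20% of data is missing". If that is met, "the recorded reasons for missing data will be assessed, and data at the three time points imputed in accordance with those reasons", and "This imputed dataset will be the basis of a sensitivity analysis". The section gives no imputation model, assumed values, number of imputations or combining rule. It does not say whether the 20% is taken over both arms together or within each, or which patients form the denominator.

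Section 2.7 raises the sample size from 364 to 406 on this ground: "Further allowing for up to 10% missing outcome data, e.g. due to the patient being too sick".

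Section 3.3 scores physical and role function as zero when the reason for a missing score is intensive care or "having died prior to the questionnaire being due". Such patients are treated as having completed the scale, and the number of zeros is reported by group. The rule is limited to two scales. No last assessment is given. Its stated aim is to stop the analysis model from filling in these values.

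Section 6.3 fits a mixed model to whatever is available at three weeks, six weeks and three months, with a single treatment coefficient. In section 8, Table 2 has a row labelled "Missing outcome data imputed" with no condition attached. For the longer term, section 6.7 says that "the mean response for LAO and OO groups at each assessment point up to 24 months will be presented graphically".

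**The concern.** The mixed model handles an unobserved score as missing at random given the patient's other scores and covariates. The SAP itself expects some scores to be missing through illness, which is where that assumption is least safe. The zero rule deals with intensive care and death. A patient who is too ill to respond on a ward or at home gets no correction, and section 6.6 looks at such patients only above the trigger.

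The trigger is also the wrong kind of criterion. Bias in the treatment effect comes mainly from a difference between arms in how many ill patients are missing, or in how ill they are. A threshold on the amount missing does not detect either. Patients scored zero count as completers, so they appear not to count towards the 20%, which makes the trigger harder to reach.

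If the analysis does run, nothing provides for imputation uncertainty. The rule for turning reasons into values is left to be settled once the data are in hand. That falls short of the SAP's aim in section 1 that another statistician could carry out the analysis from the document.

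**Working it through.** **1. The plan's own figures.** Section 2.7 gives 0.4 × 0.85 = 0.34 SD, 90% power and 5% significance (taken as two-sided). Then n = 2 × (1.960 + 1.282)² / 0.34² = 181.8, so 182 per arm, as stated. With 10% missing, 182 / 0.9 = 202.2, so 203 per arm and 406 in total, as stated.

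**2. What the trigger lets through.** 0.20 × 406 = 81.2. Up to 81 patients could lack a score at a time point without setting off the imputation, against about 41 (0.10 × 406) at the planned 10%.

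**3. Bias below the trigger.** Let D be the shortfall of the true scores of missing patients below what the model predicts for them, and p₁ and p₂ the proportions missing in the two arms.

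- Bias at one time point = D × (p₁ − p₂), in favour of the arm with more missing.
- Assumed: 8% v 18% missing (13% overall with equal arms) and D = 25 points. Neither the overall figure nor either arm exceeds 20%.
- Bias at that time point = 25 × (0.18 − 0.08) = 2.5 points.
- The primary coefficient is roughly the average of three time-specific differences. With one time point affected, 2.5 / 3 ≈ 0.8 points. With all three affected equally, 2.5 points.

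For scale, the SAP's minimum important difference is 0.4 SD, but it gives no SD in points. With an assumed SD of 22 this is 0.4 × 22 = 8.8 points, and with 15 to 25 it is 6 to 10. So 0.8 to 2.5 points is about 9% to 28% of it at SD 22. A 25-point deficit is then 25 / 22 ≈ 1.1 SD, which is severe.

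A range in SD units, for splits that average exactly 20% and so do not exceed the trigger if it is taken over both arms:

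| Missing, arm v arm | Assumed deficit (SD) | Bias at that time point (SD) |
|---|---|---|
| 20% v 20% | 0.25 to 1.0 | 0 |
| 25% v 15% | 0.25 to 1.0 | 0.025 to 0.10 |
| 30% v 10% | 0.25 to 1.0 | 0.05 to 0.20 |

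These are divided by three if only one assessment is affected. The first row assumes the same deficit in both arms. The bias follows the imbalance, which the trigger does not measure.

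**4. If one completed dataset were analysed as observed.** Assume one time point, no covariates, data missing completely at random and a fraction f = 0.20 missing.

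- Random-draw imputation: true SE / reported SE = √(1/(1 − f) + f) = √(1.25 + 0.20) = 1.204. Actual type I error = 2 × (1 − Φ(1.96 / 1.204)) = 10.4%.
- Mean fill-in: ratio = 1/(1 − f) = 1.25. Actual type I error = 2 × (1 − Φ(1.96 / 1.25)) = 11.7%.

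**5. If the zero rule ran on to 24 months.** The SAP gives no expected mortality or long-term score. With assumed survivor means of 70 to 90 and deaths of 20% to 40%, plotted means would be between 70 × 0.60 = 42 and 90 × 0.80 = 72. A mortality difference of 7 percentage points, the equivalence bound in section 6.4.8, would alone appear as 0.07 × 70 = 4.9 to 0.07 × 90 = 6.3 points of function.

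**The case against.** The plan has real safeguards. Section 6.2 and Table 2 report the number providing data by group at each primary assessment, the CONSORT diagram shows losses to follow-up, and zeros are counted by group. Death and intensive care are already handled in the primary analysis. The 10% in section 2.7 is a power allowance and not a threshold for sensitivity analysis, so 20% does not contradict it. Table 2 is an empty shell from which a conditional row can be dropped. Imputing by recorded reason already permits low scores for ill patients.

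All of this stands, but it shows only that an imbalance would be visible. Reporting counts does not show how far the estimate could move.

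Three stronger readings are tempting and are not supported:

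- A reader might infer that the SAP commits to single imputation. The basis is one singular noun, and the method is simply not stated. The figures in step 4 are therefore conditional, and they ignore the correlated repeated assessments in the primary model. Table 2 shows an interval and no p-value for this analysis.
- A reader might infer that imbalance below the trigger would go unseen. The counts by group rule that out.
- A reader might infer that the 24-month physical and role function plots count deaths as zero. Section 3.3 ties the rule to the model, which uses only the three early assessments, and section 6.7 plots means without mentioning zeros. Whether deaths enter is unclear. Those plots are exploratory and belong to the later paper, so they cannot affect the primary result.

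**Conclusion.** The point holds for the trigger and for the missing specification. The one planned test of the missing-at-random assumption may not run in a situation the SAP anticipates, and a difference between arms plays no part in deciding whether it does. Under the assumed 8% v 18% missing and 25-point deficit, the untested bias in the primary estimate is about 0.8 points with one assessment affected and up to 2.5 with all three. That is modest to material against an important difference of 6 to 10 points (SD assumed 15 to 25), and it would be smaller with milder deficits. The effect on type I error, roughly 10% to 12% at 20% missing, arises only if a single completed dataset were treated as observed, which the SAP neither says nor excludes.

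The open-ended zero rule is a secondary ambiguity that concerns exploratory plots only.

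**What to change.** In section 6.6, remove the 20% condition so that the analysis is always run, as the unconditional row in Table 2 already implies. State the imputation model and its variables, use multiple imputation (20 or more datasets) combined by Rubin's rules, and subtract a pre-specified range of amounts from the imputed scores of patients missing through illness. Let those amounts differ between arms, and report how the treatment effect and its interval change across the range. State the denominator used for reporting the percentage missing, and give that percentage by arm.

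In section 3.3, state that the zero rule applies to the three-week, six-week and three-month assessments. In section 6.7, plot later physical and role function means among survivors, beside the proportion alive in each group.

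No new data are needed. The cost is revised SAP wording and a little extra programming and analysis.
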